9.2.3.2 Initial Onset of End-Stage Renal Disease (ESRD)

Subjects will be monitored for the initial onset of end-stage renal disease from the first day of the treatment period through Week 4 of the follow-up observation period.

ESRD is defined as the start of maintenance dialysis for at least 1 month, renal transplantation, or a sustained eGFR of $< 15 \text{ mL/min/1.73 m}^2$ (this should be confirmed by remeasurement by the central laboratory after at least 30 days but preferably within 60 days; the results of measurements taken within 30 days of the assessment time point at which this criterion was first met may not be used for this assessment). The (sub) investigator will record the results in the case report form.

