12.1 Discontinuation Criteria

Subjects meeting any of the following discontinuation criteria will be discontinued from the study.

- (1) If the subject requests discontinuation.
- (2) If it is determined that the subject is clearly ineligible to participate in the study.
- (3) If the (sub) investigator determines that it would be difficult to continue the study because of the emergence of, for example, an adverse event.
- (4) If the (sub) investigator determines that it would not be appropriate to continue the study because of a worsening of the patient's primary disease.
- (5) If it is discovered that the subject is pregnant.
- (6) If the (sub) investigator determines that the study should be discontinued for some other reason.

Rationale

(1)-(6) These criteria were established to allow the study to be ethically conducted and in consideration of subject safety.

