13.3.2 Efficacy

The following statistical procedure will be used for efficacy. Furthermore, subgroup analyses will be performed for some of the endpoints using stratification factors such as the eGFR (≥ 30 mL/min/1.73 m² and < 45 mL/min/1.73 m²; ≥ 45 mL/min/1.73 m²).

(1) Primary endpoint:

Analysis method for the proportion of subjects achieving a 30% decline in the eGFR

1) Primary analysis

The point estimate for the intergroup difference in the proportion of subjects achieving a 30% decline in the eGFR will be calculated, along with the 95% confidence interval using the Farrington-Manning method.

2) Secondary analysis

An adjusted analysis based on a logistic regression analysis model (with treatment group as a factor) that includes randomization factors as covariates will be performed for the proportion of subjects achieving a 30% decline in the eGFR, and the odds ratio and the 95% confidence interval thereof will be calculated.

Furthermore, in the aforementioned primary and secondary analyses, data will be replaced using a multiple imputation method. Detailed information about, for example, sensitivity analysis will be included in the statistical analysis plan.

(2) Analysis methods for the secondary and other endpoints

1) The Proportion of subjects achieving a 40% decline in the eGFR

An analysis similar to that performed for the proportion of subjects achieving a 30% decline in the eGFR will be performed for the proportion of subjects achieving a 40% decline in the eGFR.

2) Other efficacy endpoints

1. Change and percent change in the eGFR
2. Percent change in the urine ACR (first morning void urine)
3. Change in the HbA1c
4. Change in fasting blood glucose
5. Change in blood pressure (systolic blood pressure, diastolic blood pressure)
6. Change and percent change in lipids (HDL-C, fasting neutral lipids)
7. Change and percent change in body weight
8. Change in the fasting urine glucose/creatinine ratio

The aforementioned outcome measures for the other efficacy endpoints will be evaluated using a mixed model for repeated measures that includes treatment group, baseline value, visit, and treatment group-by-visit interactions. For the urine ACR, furthermore, the log-transformed urine ACR will be used.

3) Event endpoints

1. Composite endpoint of end-stage renal disease (ESRD), doubling of serum creatinine, renal death, and cardiovascular (CV) death
2. Composite endpoint of CV death and hospitalized congestive heart failure

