HbA1c	Hemoglobin A1c
hCG	Human chorionic gonadotropin
HDL-C	High density lipoprotein cholesterol
HIV	Human Immunodeficiency Virus
LOCF	Last observation carried forward
NSAID	Non-steroidal anti-inflammatory drugs
NYHA	New York Heart Association
PPS	Per Protocol Set
PTP	Press-through sheets
PVD	Peripheral Vascular Disease
SGLT	Sodium glucose co-transporter
SMBG	Self-monitoring of blood glucose
t _{1/2}	Terminal elimination half-life
t _{max}	Time to reach maximum plasma concentration

Definition of Terms

Term	Definition
Screening period	The period from the first day of the screening period until the completion of the scheduled tests on the first day of the run-in period, 4 weeks at most.
Run-in period	The 2-week period from the completion of the scheduled tests on the first day of the run-in period until the completion of the scheduled tests on the first day of the treatment period.
Treatment period	The period from the completion of the scheduled tests on the first day of the treatment period until the completion of the scheduled tests on the last day of the treatment period (Week 104 of the treatment period or the day of treatment period discontinuation).
Follow-up observation period	The 4-week period from the completion of the scheduled tests on the last day of the treatment period.
Pre-treatment period discontinuation	Discontinuation in the period between informed consent acquisition and the end of the run-in period.
Treatment period discontinuation	Discontinuation during the treatment period
Proportion of subjects achieving a 30% decline in the eGFR	The proportions of subjects at the end of the treatment period with a decline of 30% in the eGFR or more compared to the average of the values on the first days of the run-in and treatment periods
Proportion of subjects achieving a 40% decline in the eGFR	The proportions of subjects at the end of the treatment period with a decline of 40% in the eGFR or more compared to the average of the values on the first days of the run-in and treatment periods

1. Introduction

This document describes the sponsor's plans for the statistical analyses in the "a randomized, double-blind, placebo-controlled study to evaluate efficacy and safety of canagliflozin (TA-7284) in patients with diabetic nephropathy," and covers the information that is included in the study protocol, but in greater detail.

[figure not shown]
2. Study Objective And Study Design

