6.2.1. Tabulation by eGFR Assessment Time Point

When tabulating the eGFR at each assessment time point, data that fall within the allowable time windows defined in “Table 6.2: Test/Observation Schedule Allowable Time Windows” will be used. For data that have been reported as having been collected at treatment period discontinuation, data that were collected within the allowable time window for the day of treatment period discontinuation will be used. Although a data tabulation at discontinuation will not be performed, data that have been collected within the allowable time window for the day of treatment period discontinuation that are also within the allowable time window for the time point in question will as a rule be used as data for that time point. In addition, if multiple measurements have been taken within an allowable time window, data from the test that was performed on the day closest to the target day will be used. If there are multiple measurements, and the difference in the numbers of days between the day of each measurement and the target day are the same, then the data that were collected earlier will be used.

6.2.2. Tabulation of the eGFR at Each Assessment Time Point When Imputing Data Outside the Allowable Time Window

When tabulating the eGFR data for each assessment time point, the data stipulated in 6.2.1 will be combined with data imputed by means of multiple imputation (██████████) for data for which the assessment time point was outside the allowable time window. A linear regression model with the data at each assessment time point from the first day of the treatment period until Week 88 of the treatment period as the explanatory variable will be used to replace missing values for each assessment time point from Week 4 of the treatment period through Week 104 of the treatment period. It will be assumed that the pattern of missing values is non-monotonic.

6.2.3. Tabulation of Endpoints Other Than the eGFR and Urine ACR at Each Assessment Time Point

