6.2.4. Tabulation of the Urine ACR Endpoints at Each Assessment Time Point

When tabulating the urine ACR endpoints at each assessment time point, if the date of the visit falls within the allowable time window defined in “Table 6.2: Test/Observation Schedule Allowable Time Windows,” then data that have been collected within a 1-week period that includes the visit day will be used as data for that time point. Also, if the day of the visit at discontinuation falls within the allowable time window of the day of discontinuation in the treatment period and the allowable time window for the time point data, then data that were obtained within a 1-week period that includes the day of the visit at discontinuation will be used as the data for that time point. Data will not be replaced with data from outside the allowable time windows. In addition, if multiple measurements were taken within the allowable time window, then the visit day that was closest to the target date will be used. If the difference (in the number of days) between the day of the measurement and the target day is the same for each of two measurements, then the earlier day will be used.

6.3. Handling of eGFR Data at the End of the Treatment Period (Analysis of 7.6.1.3)

When tabulating eGFR data at the end of the treatment period, the data collected at Week 104 of the treatment period, as defined in “Table 6.2: Test/Observation Schedule Allowable Time Windows” will be used. However, if any data from Week 104 of the treatment period are missing, then these data will be imputed as indicating that an eGFR decline has occurred.

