7.6. Analysis of Efficacy

7.6.1. Primary Endpoints

7.6.1.1. Primary Analysis

Analysis population(s): FAS, PPS

Analysis parameter(s): Proportion of subjects with a decline of 30% in the eGFR at Week 104 of the treatment period

Analysis method:

In accordance with “6.2.2. Tabulation of the eGFR at Each Assessment Time Point When Imputing Data Outside the Allowable Time Window,” a dataset will be prepared using [REDACTED]. The estimated values from this dataset, and the variance thereof, will be combined using Rubin’s rule, and the proportion of subjects with a decline of 30% in the eGFR at Week 104 of the treatment period, and the 95% confidence interval thereof, will be shown for each treatment group. The point estimate for the difference between the groups (placebo group minus TA-7284 group) and the 95% confidence interval according to the Farrington-Manning method will also be shown.

Listings

Analysis population(s): Randomized subjects

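### Subjects with recorded renal failure and no Week 104 eGFR have the primary outcome imputed, with no visible rule counting them as declined; the likely effect is small and the remedy cheap

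*SAP*

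**What the plan says.** The primary analysis (SAP 7.6.1.1) takes as its parameter the "Proportion of subjects with a decline of 30% in the eGFR at Week 104 of the treatment period". Missing values are handled under SAP 6.2.2: "A linear regression model with the data at each assessment time point from the first day of the treatment period until Week 88" supplies the predictors, and the model "will be used to replace missing values for each assessment time point from Week 4 of the treatment period through Week 104". The logistic analysis (7.6.1.2) uses the same dataset, as do the 40%-decline versions of both (7.6.2.1). Protocol 13.3.2 agrees: "in the aforementioned primary and secondary analyses, data will be replaced using a multiple imputation method". Neither document makes a visible exception for renal failure, and no event indicator is named as a predictor.

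Renal failure is recorded separately. In Protocol 9.2.3.2, "ESRD is defined as the start of maintenance dialysis for at least 1 month, renal transplantation, or a sustained eGFR" below 15, confirmed at least 30 days later. Protocol 9.2.3.3 defines confirmed creatinine doubling and 9.2.3.4 renal death. These enter only the event endpoints (SAP 6.4 and 7.6.2.4).

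One analysis does count these subjects as declined. For Other Analysis 1 (SAP 6.3 and 7.6.1.3), if the Week 104 value is missing, "then these data will be imputed as indicating that an eGFR decline has occurred", whatever the reason.

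The last day of the treatment period is defined as "Week 104 of the treatment period or the day of treatment period discontinuation", but the SAP analyses score Week 104 only. A low eGFR at discontinuation is therefore not itself the outcome unless it falls in the Week 104 window (days 715 to 742, SAP Table 6.2).

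**The concern.** Protocol 12.1 lets the investigator withdraw a subject when it would "not be appropriate to continue the study because of a worsening of the" primary disease. Subjects in renal failure are therefore among those likely to lack a Week 104 eGFR. For them the answer to the primary question is already on the case report form, yet the plan draws it at random from a model that sees only earlier eGFR values.

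Protocol 5.4.1.1 chose the 30% decline as a surrogate for end-stage kidney disease. Scoring a subject with actual ESRD as not declined, even in some of the imputed datasets, works against that rationale. It lowers the decline proportion in whichever arm has more such subjects.

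**Working it through.** The documents give no figure for this point. The sample-size rationale is not shown, so there is no planned event rate or effect to reproduce. All slopes, noise levels and failure counts below are assumptions.

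**1. Do these events imply a 30% decline?** The eGFR formula (SAP 4.8) has creatinine to the power −1.094.
- Doubling: 2^−1.094 = 0.468, a 53.2% fall.
- eGFR below 15: entry requires at least 30 on the first run-in day. A value of 15 would be less than a 30% decline only if the two-visit baseline mean were below 15/0.70 = 21.4, and less than a 40% decline only if it were below 15/0.60 = 25.

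Both laboratory criteria are therefore in practice beyond 30% and 40%.

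**2. Is the low value in the imputation model?** After Week 52, eGFR is scheduled at Weeks 64, 76, 88 and 104 (Protocol 9.2.3.1). A discontinuation value goes to the window it falls in (SAP 6.2.1).
- Days 379–714 form 12 windows of 28 days (336 days). Three of them (Weeks 64, 76, 88) have a scheduled eGFR. The other 9 × 28 = 252 days do not, so a value there has almost no counterpart in other subjects.
- Days 631–714 (Weeks 92–100) lie after Week 88, outside the stated predictors. Example: an eGFR below 15 at discontinuation on day 650, confirmed at the follow-up visit at least 30 days later, is recorded ESRD that does not inform the Week 104 draw.

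**3. Chance that one draw shows no 30% decline.** Let b be baseline, m the imputation mean and s the residual SD. Then P = 1 − Φ((0.70b − m)/s). If the last value is at doubling and the mean stays there, m = 0.468b. If it regresses 20% toward 0.9b, m = 0.8 × 0.468b + 0.2 × 0.9b = 0.555b.

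| b | m = 0.468b, s = 4 to 12 | m = 0.555b, s = 4 to 12 |
|---|---|---|
| 30 | 4% to 28% | 14% to 36% |
| 45 | 0.5% to 19% | 5% to 29% |
| 60 | 0% to 12% | 1.5% to 23% |
| 75 | 0% to 7% | 0.3% to 18% |

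**4. Simulation, gradual decline.** The settings were 150 per arm; baseline uniform on 30–90; mean slope −4 or −5 per year (SD 4 or 5); visit noise SD 3 to 6; 0% to 10% fast progressors; 12% other dropout. A multivariate normal model stood in for the redacted method. There were 3 to 23 renal failures without a Week 104 value per 300. They were scored as not declined in 0.1% to 6% of draws with the failing eGFR in the model, and in 0.1% to 8% without it. The largest expected count was 23.1 × 0.0591 = 1.4 subjects per 300, or 1.4/150 = 0.9 points if all were in one arm.

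**5. Abrupt fall.** Where eGFR was assumed to fall over the 12 weeks before loss, simulation gave 24% to 43% of draws scored as not declined. With k such failures in an arm and mean probability q, that arm's proportion is too low by k × q/150.
- 3 on placebo and 1 on TA-7284, q = 0.24: placebo 3 × 0.24/150 = 0.48 points; difference 2 × 0.24/150 = 0.32 points.
- 6 and 3, q = 0.43: placebo 6 × 0.43/150 = 1.72 points; difference 3 × 0.43/150 = 0.86 points.

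The simulated shift in the difference was 0.3 to 0.8 points.

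**6. Against sampling error.** With assumed proportions of 18.1% and 9.8%, SE = √(0.181 × 0.819/150 + 0.098 × 0.902/150) = 4.0 points. With 20.8% and 11.05% it is 4.2 points.

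**The case against.** The strongest reply is that the plan largely handles these subjects already. A fall first seen at Week 104 leaves nothing to impute. A fall seen at Week 88 or earlier is in the model. Remeasurement is required after a qualifying value (schedule footnote g), and discontinuation tests are due within 7 days (Protocol 12.2). Other Analysis 1 counts every missing Week 104 value as declined. Renal events are analysed in their own right, and adding them to an eGFR endpoint is a choice of composite strategy.

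Much of this stands. A reader might infer that no analysis counts these subjects as declined; SAP 6.3 and 7.6.1.3 show otherwise. A reader might also infer that known failures simply are scored as non-decliners. Under multiple imputation it is a probability per draw, usually small because the preceding values are already low.

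Three things remain. Dialysis or transplantation can be recorded without a low eGFR in the model. Discontinuation values on days 631–714 are not predictors, and values in other windows without a scheduled eGFR are hard to use. And Other Analysis 1 also counts unrelated dropouts as declined, so it is a sensitivity analysis and does not repair the primary one.

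**Conclusion.** The gap is real in the visible text, and its expected effect is small. The risk of mis-scoring is near zero for steady progressors with low values in the model. It is larger for abrupt or late falls, for low baseline eGFR, and where the failing value is not a usable predictor. The difference moved by less than 1 percentage point in all simulated settings, well inside one standard error. A shift of 1 point would need a net excess of 1.5 expected mis-scored subjects in one arm (0.01 × 150).

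Two stronger readings are not supported. One is that the 24–43% range is typical: it comes only from assumed abrupt falls, and the documents do not say how failures would present. The other is that the plan is biased against the drug: the shift is toward zero only if placebo has more of these failures, and no rates are given.

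The imputation method and SAP appendices are redacted, and SAP section 6 excepts matters decided by the sponsor's case review board. A rule may exist there; if so, 6.2.2 should state it. Priority: minor.

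**What to change.** In SAP 6.2.2 and 7.6.1.1, and through them 7.6.1.2 and 7.6.2.1, state before database lock:

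- A subject with maintenance dialysis, transplantation, confirmed eGFR below 15, confirmed creatinine doubling or renal death recorded before Week 104, and no Week 104 eGFR, is set to decline (30% and 40%) in every imputed dataset. Only the remaining missing values are imputed.
- An eGFR measured after the start of maintenance dialysis or after transplantation is treated the same way, so that it cannot score as no decline.
- Other Analysis 1 (7.6.1.3) stays as a sensitivity analysis. Non-renal death stays as the plan has it.

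The cost is a short addition to the SAP and a few lines of code, since the events are already on the case report form. The downside is that the endpoint becomes a composite for a handful of subjects, which the SAP should say openly.

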The change in the eGFR when TA-7284 was administered in combination with metformin for 104 weeks was investigated in the CANTASA-SU study (study [REDACTED]) in type 2 diabetes patients, in which glimepiride was used as the control. Although the TA-7284 group exhibited a transient decrease in the eGFR immediately after administration, a constant eGFR level was subsequently maintained, and the change in the eGFR from baseline was -2.7 ml/min/1.73 m² (95% confidence interval, -3.5 to -1.9) in the TA-7284 100 mg group and -3.9 ml/min/1.73 m² (95% confidence interval, -4.7 to -3.0) in the TA-7284 300 mg group. In the glimepiride group, on the other hand, the eGFR decreased at a constant rate after the start of the study, and the change in the eGFR from baseline was -5.4 ml/min/1.73 m² (95% confidence interval, -6.2 to -4.5). These results suggested that the long-term use of TA-7284 may inhibit the reduction in the eGFR compared to patients receiving glimepiride, in whom the eGFR continues to fall at a constant rate.

Safety

There are at present no results from clinical studies in patients with Stage 3 diabetic nephropathy (overt nephropathy). The results of Japanese clinical pharmacology studies conducted in type 2 diabetes patients with moderate renal impairment and Japanese clinical studies in type 2 diabetes patients are described below.

In a Japanese phase 2 dose-finding study and phase 3 studies that were conducted in type 2 diabetes patients, 953 adverse reactions (including clinical laboratory abnormalities) were reported in 474 of 1629 subjects (29.1%). The most common adverse reactions included asymptomatic hypoglycemia, hypoglycemia, pollakiuria, increased blood ketone bodies, and constipation. The package insert lists the following as "clinically significant adverse reactions": hypoglycemia, dehydration, ketoacidosis, septicemia, and pyelonephritis. In addition, the following are listed as "other adverse reactions" that occur in at least 1% of patients: constipation, thirst, cystitis, pollakiuria, vulvovaginal candidiasis, ketosis, asymptomatic hypoglycemia, and increased blood ketone bodies.

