9.2.4.6 Resting Standard 12-Lead ECG

A resting standard 12-lead ECG will be measured at the subject visits on the first day of the run-in period, the first day of the treatment period, and Weeks 24, 52, 76, and 104 of the treatment period (or at treatment period discontinuation). The results of, for example, the arrhythmia and waveform diagnoses from the ECG results will be comprehensively assessed and classified according to the following 3 levels, and the result entered into the case report form.

- (1) Normal
- (2) Abnormal, NCS (Clinically insignificant abnormality)
- (3) Abnormal, CS (Clinically significant abnormality)

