When tabulating the data for endpoints other than the eGFR and urine ACR, data that have been collected within the allowable time windows defined in “Table 6.2: Test/Observation Schedule Allowable Time Windows” will be used. For data that have been reported as having been collected at treatment period discontinuation, data that were collected within the allowable time window for the day of treatment period discontinuation will be used. Although a data tabulation at discontinuation will not be performed, data that have been collected within the allowable time window at discontinuation that are also within the allowable time window for the time point in question will be used as data for that time point. Data will not be replaced with data from outside the allowable time windows. In addition, if multiple measurements have been taken within an allowable time window, data from the test that was performed on the day closest to the target day will be used. If the differential number of days from the

reference date is equal, the data obtained before the reference date will be used to evaluate efficacy, and the data obtained after the reference date will be used to evaluate safety.

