7.7.4. Clinical Laboratory Tests

Analysis population(s): Safety analysis set

Analysis parameter(s): Hematology test parameters, blood biochemistry test parameters (except for the parameters for the efficacy assessments), urinalysis (quantitative) (except for the parameters for the efficacy assessments), urinalysis (qualitative), renal function biomarkers

Analysis method:

For the analysis parameters other than urinalysis (qualitative), descriptive statistics will be presented by treatment group for the values at each assessment time point and the changes therein. For the urinalysis (qualitative) parameters, the number and proportion of subjects at each assessment time point will be presented by treatment group and treatment category ((-), (+/-), (1+), (2+), (3+), (4+)). The number and proportion of subjects at each measurement time point will be presented for the change in treatment category compared to the first day of the treatment period, as well.

For analysis parameters other than urinalysis (qualitative) parameters, shift tables will be prepared by treatment group showing the treatment categories (low, normal, high) at the first day of the treatment period and at each assessment time point. For urinalysis (qualitative) parameters, shift tables will be prepared by treatment group showing the treatment categories (normal, abnormal) at the first day of the treatment period and at each assessment time point.

Listings

Analysis population(s): Safety Analysis Sets

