7.7.6. Resting Standard 12-Lead ECG

Analysis population(s): Safety analysis set

Analysis parameter(s): Results of ECG diagnosis (normal, abnormal but not clinically significant, abnormal and clinically significant)

Analysis method:

For each analysis parameter, the frequency of each assessment result (normal, abnormal but not clinically significant, abnormal and clinically significant) at each measurement time point will be tabulated for each treatment group, and shift tables showing the assessment results for the first day of the treatment period and the assessment time points will be prepared.

Listings

Analysis population(s): Safety Analysis Sets

8. Software Used

The SAS Windows version (release 9.4) will be used for statistical analysis.

9. Changes to Statistical Analysis Plan From The Protocol

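### Laboratory, vital-sign and ECG results are tabulated visit by visit only, so values taken at discontinuation can be displaced, dropped or scattered in the safety tables

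*SAP*

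**What the plan says.** **Collection.** The protocol requires safety laboratory tests (9.2.4.1), vital signs (9.2.4.4) and ECG (9.2.4.6) at treatment discontinuation. Blood tests and vital signs are scheduled every four weeks to Week 52, then at Weeks 64, 76, 88 and 104. On-treatment ECGs are scheduled at "Weeks 24, 52, 76, and 104 of the treatment period (or at treatment period discontinuation").

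**Selection.** SAP 6.2.3 covers all endpoints other than eGFR and urine ACR and has its own tie rule for safety data, so it applies here. It sets four rules:
- No separate table: "Although a data tabulation at discontinuation will not be performed".
- Discontinuation data enter a table only through a visit window: data "that are also within the allowable time window for the time point in question will be used as data for that time point".
- Nothing is brought in from elsewhere: "Data will not be replaced with data from outside the allowable time windows".
- If a window holds several results, "data from the test that was performed on the day closest to the target day will be used". The later value is preferred for safety only when two results are equally far from the target.

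**Presentation.** SAP 7.7.4 gives laboratory statistics by time point, with shift tables in the categories "low, normal, high) at the first day of the treatment period and at each assessment time point". SAP 7.7.5 gives vital signs by time point. SAP 7.7.6 gives ECG results whose frequency "at each measurement time point will be tabulated for each treatment group", with shifts to each time point. Listings are planned in all three sections. None of them plans a last on-treatment, worst-value or any-time summary.

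**The concern.** For a subject who stops early, the discontinuation sample is the last one taken in the treatment period and may be the most informative. The plan collects it but guarantees it no place in a by-arm table.

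This matters for this drug class. Protocol section 1(3), Safety, reports that the package insert lists "hypoglycemia, dehydration, ketoacidosis, septicemia, and pyelonephritis" as clinically significant adverse reactions. It also reports increased blood ketone bodies among the most common reactions in the Japanese studies. Ketone bodies and potassium are in the laboratory panel. If discontinuation values are displaced or scattered, the shift tables cannot show by arm how many subjects left treatment with an abnormal value, or had one at any time on treatment.

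**Working it through.** The plan states no figure to reproduce, so the check is a count of days from SAP Table 6.2.

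**Inputs.** The Week 4 window is days 14-42. Every later window for Week w runs from day 7w − 13 to day 7w + 14 (Week 52: 351-378; Week 104 opens on day 715). The windows are contiguous from day 14. The table lists every fourth week, including Weeks 56, 60, 68, 72, 80, 84, 92, 96 and 100, when none of these tests is scheduled. The count covers days 1-714, before the Week 104 window opens.

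**Reading A: a row for every window in Table 6.2.** Only days 1-13 are uncovered, for every test: 13/714 = 1.8%.

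**Reading B: rows only for weeks when the test is scheduled.**
- *Blood tests and vital signs.* Covered: days 14-378 (365 days) plus Weeks 64, 76 and 88 (3 × 28 = 84), in total 449. Uncovered: 714 − 449 = 265, and 265/714 = 37.1%. The gaps are days 1-13, 379-434, 463-518, 547-602 and 631-714 (13 + 56 + 56 + 56 + 84 = 265). From day 14 to day 378 there is no gap. From day 379 to day 714, 252 of 336 days (75%) are uncovered.
- *ECG.* Covered: Weeks 24, 52 and 76 (3 × 28 = 84). Uncovered: 714 − 84 = 630, and 630/714 = 88.2%.

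**Scatter under Reading A.** An ECG taken at discontinuation on day 300 falls in the Week 44 window (295-322), where no ECG is scheduled. Its row would hold only subjects who happened to stop, or to have an extra ECG, in those four weeks.

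**Displacement under either reading.** Suppose the Week 52 visit is on day 364 and the subject stops on day 375. Both dates lie in 351-378. The distances from target are 0 and 11 days, so the day-375 results are not tabulated. If each scheduled visit falls on its target day, a discontinuation up to 14 days later in the same window loses its values. For blood tests and vital signs this covers 16 windows × 14 = 224 of the 714 days.

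**Illustration in subjects.** The documents as supplied give no discontinuation rate. Assume that 10% to 30% of 300 subjects (30 to 90) stop evenly over days 1-714. Under Reading B the untabulated discontinuation sets would number 30 × 265/714 = 11.1 to 90 × 265/714 = 33.4 for blood tests, and 30 × 630/714 = 26.5 to 90 × 630/714 = 79.4 for ECG. Under Reading A they would number 0.5 to 1.6. Displacement is not included.

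**The case against.** The strongest answer is the adverse event route. Protocol 9.2.4.8 has the investigator handle every clinically significant abnormality as an adverse event. Its criteria include treatment given, or study drug withdrawn or discontinued, because of the abnormality. These events are reported by arm with incidence per 1000 person-years, including those leading to discontinuation (SAP 7.7.1.1) and volume depletion, diabetic ketoacidosis and renal-related events (SAP 7.7.3). No visit window governs those counts. Doubling of serum creatinine is also a by-arm event endpoint (SAP 7.6.2.4). This stands. A reader might infer that a subject stopped for ketosis or dehydration drops out of the comparison between arms; the documents do not support that. The route does depend partly on investigator judgement and yields coded terms, so it does not replace shift tables against laboratory reference ranges.

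Second, SAP 6.2.3 does not limit the time point to weeks when the test is scheduled, and Table 6.2 lists every fourth week. Read literally, almost no day is uncovered. This also stands. A reader might infer that 37% of discontinuation blood tests and 88% of discontinuation ECGs will be lost. Those are the upper ends of a range on one reading, and they count days.

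Third, a reader might conclude that the tables describe mainly subjects who tolerated the drug. That is not supported: subjects who stop still contribute their earlier visits, and for blood tests and vital signs every window from day 14 to day 378 belongs to a scheduled visit.

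Fourth, Protocol 13.3.3 itself specifies summaries by time point, and the SAP follows it. There is no contradiction, and the remedy is an addition.

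**Conclusion.** The point holds as a gap in safety reporting. Under the stated rules a discontinuation value can be displaced by one nearer the target day, lost on days 1-13, or, because the SAP does not say whether unscheduled weeks get rows, left out or spread over very small rows. The uncovered share of days 1-714 is 1.8% to 37.1% for blood tests and vital signs and 1.8% to 88.2% for ECG. How many subjects that means depends on when they stop, which the plan does not predict.

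The gap is largest for ECG and, for blood tests and vital signs, after Week 52. On days 14-378 the latter can lose a discontinuation value only through displacement. The loss concerns the laboratory, vital-sign and ECG summaries and shift tables, and mainly abnormalities not reported as adverse events. The absence of a last-value or worst-value summary does not depend on which reading of the windows is right. The primary analysis is unaffected.

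**What to change.** Keep the visit-wise tables and add to SAP 6.2.3 and 7.7.4 to 7.7.6, by treatment group:

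1. A last on-treatment value row that includes the discontinuation visit.
2. A shift table from the first day of treatment to the worst on-treatment value, using all central-laboratory, vital-sign and ECG results, including discontinuation and unscheduled ones.

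Define on-treatment to match the SAP's treatment period, so that the discontinuation visit counts. State for each parameter whether worst means highest, lowest or both. SAP 7.7.5 sets no categories for vital signs, so either specify them or summarise the worst change. State also whether weeks with no scheduled test get rows in the existing tables.

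The cost is SAP wording and one extra set of tables from data already collected. The downside is that any-time counts rise with length of follow-up, so exposure by arm should be printed beside them.
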